4.5 Early Withdrawal of Subjects

4.5.1 When and How to Withdraw Subjects

Subjects participate in a "one-time" event (i.e., surgery) as part of this study and are not expected to be withdrawn because of subsequent post-surgical conditions and/or scenarios (e.g. the need for alternative and/or additional treatment). Subjects may withdraw their consent at any time prior to surgery. Subject data collected per protocol may subsequently not be included in the final analysis, if IV administration of ABY-029 is found not to have occurred at the proper dose (237 μ g, 711 μ g or 1.42mg, depending on the dose group) approximately 1-3 hours prior to surgery or the definitive post-operative diagnosis does not meet the presumed entry criteria.

4.5.2 Data Collection and Follow-up for Withdrawn Subjects

No post-operative end-points or follow-up information is needed to meet study objectives; hence, consenting subjects who complete surgery will not be lost to follow-up.

5 Study Drug

5.1 Description

Patients will be administered ABY-029 by intravenous injection approximately 1-3 hours prior to induction of anesthesia. The range of approximately 1-3 hours is acceptable given pre-clinical data indicating that imaging signal levels appear to be stable over this time period. Time from ABY-029 administration to surgery is collected. Subjects are considered enrolled in the study once ABY-029 has been injected.

5.2 Treatment Regimen

Groups of up to 6 patients (as described in Section 1.5) will receive a single injection of ABY-029 at 1X or 3X or 6X of the microdose of 30 nanomoles (237 μ g). The dose will be administered by intravenous injection on the day of surgery, approximately 1-3 hours prior to the procedure.

5.3 Method for Assigning Subjects to Treatment Groups

No separate treatment groups are part of the study design.

5.4 Preparation and Administration of Study Drug

ABY-029 used in this study is stored, prepared, and dispensed by the Investigational Pharmacy at Dartmouth-Hitchcock Medical Center. (Address: Dartmouth Hitchcock Medical Center, Investigational Pharmacy, [name]; email address: [contact]; [contact]).

ABY-029 Preparation and Administration Procedures:

- 1) ABY-029 is prepared by the Investigational Pharmacy at the appropriate dose, typically on the day of or day before surgery, depending on the scheduled surgery date and time.
- 2) From the vial containing ABY-029, the required dose is withdrawn into a syringe, labeled, and placed into a light-impermeable bag.
- 3) Once prepared at the requested dose, the drug in the light-impermeable bag is either held by the Investigational Pharmacy until picked up by a member of the study team, or stored in a refrigerated and locked box in the Same Day Surgery patient holding area. The key to the lock-box is placed in an associated Acudose Unit.
- 4) The dose of ABY-029 is administered intravenously through an IV port followed by a saline flush.

Most study subjects will check in to the Same Day Surgery Program on the day of their surgery, though some may be admitted inpatients. Study subjects generally have a pre-surgical MRI. ABY-029 will be administered to patients approximately 1-3 hours prior to surgery, in the Same Day Surgery Program area, the MRI area, or in an inpatient unit. Patients will be under the care and observation of a research nurse or Same Day Surgery nurse, or by an inpatient nurse if ABY-029 is administered in the inpatient area, during the time between ABY-029 administration and the start of surgery, and will be monitored accordingly and appropriately. If ABY-029 is administered prior to the pre-surgical MRI, a research nurse will accompany the patient to the MRI and monitor the patient until he or she is in the Same Day Program holding area.

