Biodistribution of the 100X microdose of ABY-029 was assessed in normal rats and analysis was performed at 1 hour after injection. One hour post-intravenous administration of ABY-029 the rats were sacrificed by cervical dislocation, and the organs of interest were removed and then imaged on the Pearl Imaging System (LI-COR Biosciences). We found a high accumulation of ABY-029 in the liver, skin, lungs, and kidney, which are all organs with high endogenous EGFR expression and/or that are involved in the route of excretion. No significant difference occurred between ABY-029 accumulation in male and female non-sex organs, although males had slightly higher values, possibly due to size of organ versus body weight, as injected dose was normalized to body weight. Rats without brain tumors had comparably very low levels of ABY-029 accumulation in normal brain tissue, due to the blood brain barrier.

- Pharmacokinetic Study in normal rats**

Plasma pharmacokinetics of the dye was assessed as function of time by sampling blood from a jugular vein catheter at various time points after administration. Pharmacokinetic data was collected from normal Sprague Dawley rats at time points from 1 minute to 48 hour) after intravenous injection of 100X microdose ABY-029 (244.9 µg/kg). Blood plasma was read on a Fluoromax-3 fluorimeter (Horiba Jobin Yvon), a standard curve was created, and all fluorescent data was converted to concentration using the standard curve and the bi-exponential plasma curve. The plasma curve created in this study matched closely with the previously determined pre-clinical plasma curves, indicating that the physical and biological characteristics of ABY-029 were closely retained. The plasma half-life of ABY-029 in normal rats is approximately 15-20 minutes and less than 10% remains in the plasma at 24 hours and is undetectable at 48 hours. In pre-clinical rat and mouse studies, ABY-029 has been detectable in tissues (tumor, liver, kidney) for up to 72 hours.

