5.9.3 Dispensing of Study Drug

Once drug assignment is performed, a study authorized staff member (e.g., [name], his designee) will order ABY-029 through the institution's electronic medical record. This order will specify the dose of 1X (237 µg), 3X (711 µg) or 6X (1.42mg) for ABY-029. Since the concentration in each vial of ABY-029 is 1.35 mg or 5.7X, in order to conserve our supply of ABY-029 we will administer a 5.7X dose to the 6X dose group in this study, and will call this the "6X dose" throughout this protocol. One dose of ABY-029 will be administered to each subject. The investigational pharmacy pharmacist will process this order and a pharmacy technician will prepare the ABY-029 dose as described in Section 5.4 (above)

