5.9.5 Return or Destruction of Study Drug

At the completion of the study, a final reconciliation of drug shipped, drug consumed, and drug remaining will occur. This reconciliation will be logged on the drug reconciliation form, signed and dated. Any discrepancies noted will be investigated, resolved, and documented prior to return or destruction of unused study drug. Site policy (i.e., Investigational Pharmacy) is to destroy any used, open drug containers on site. Drug destroyed on site will be documented in the study files.

6 Study Procedures

This study is a Phase 0 clinical investigation of ABY-029 concentration measured/detected in brain tissue through its fluorescence emissions as an intraoperative biomarker of tumor during open cranial surgery for tumor resection. Subjects participate in a "one-time" event/visit (i.e., surgery) as part of this protocol. Images and data from the patient's pre- and post-operative MR scans are used for analysis in the study, but these acquisitions are part of the patient's standard-of-care, would occur independently of whether the participant is enrolled, and thus, are not considered to be research study visits. No post-surgical follow-up visit is part of the protocol data collection or analysis. Patients are monitored for possible adverse events for approximately 30 days through the routine follow-up under the care of the operating surgeon involved in

the study procedures, post-operatively, and subsequently through the medical record. Hence, this information is already being collected as part of standard-of-care and is available for adverse event surveillance.

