The study will be monitored by the Data, Safety Monitoring, and Accrual Committee (DSMAC) of the Norris Cotton Cancer Center at Dartmouth-Hitchcock Medical Center. All unexpected and/or serious adverse events will be reported to committee by the protocol PI or the designee, along with a determination of their relationship to study procedures. Given that brain tumor patients undergoing open surgical resection procedures present with post-operative complications and medical events that are expected, we will log and review all adverse events, but evaluate and report on only those with outcomes that would not routinely be expected in this surgical patient population to the NCCC DSMAC, along with a determination of their probable relationship to study procedures. Summaries of study enrollments, clinical status, and data will be submitted for annual review (or more frequently as required depending on enrollment patterns). In the case of any unexpected adverse events, the patient's medical record will be reviewed by a study physician, and if necessary, the patient will be examined by a study physician and appropriate medical action taken. The event will be recorded in the patient's study file with the date of occurrence, date of resolution, severity and the actions taken. Any unexpected or serious adverse events, or drug reaction beyond those expected from open-cranial brain tumor surgery that are determined likely to be related to the study procedures, will be reported to the Dartmouth IRB and the FDA as required.

9 Data Handling and Record Keeping

9.1 *Confidentiality*

Information about study subjects will be kept confidential and managed according to the requirements of the Health Insurance Portability and Accountability Act of 1996 (HIPAA). Risk of breach of confidentiality of the medical records and status of participants will be minimized. Databases which are used to store subject-sensitive information are password-protected and encrypted during file/data transfers from viewing terminals. Access will be limited to research team members who have undergone CPHS training at Dartmouth. Whenever possible and practical standard-of-care clinical data used in the research will be de-identified when under analysis.

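### Section 8 judges events that begin after the ABY-029 injection but before anesthesia by what is expected of brain-tumor surgery, so non-serious ones of an expected type need no assessment of relation to the drug

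*Combined protocol and SAP*

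**What the plan says.** Section 5.9.3 states: "One dose of ABY-029 will be administered to each subject". Section 5.4 sets the timing: "ABY-029 will be administered to patients approximately 1-3 hours prior to surgery". Section 5.1 gives the same 1-3 hours a different end point: "approximately 1-3 hours prior to induction of anesthesia". Under Section 5.4 a research, Same Day Surgery or inpatient nurse looks after the patient "during the time between ABY-029 administration and the start of surgery, and will be monitored accordingly and appropriately". It names no assessments and no recording times.

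Section 6 describes adverse-event surveillance as follows: "Patients are monitored for possible adverse events for approximately 30 days through the routine follow-up under the care of the operating surgeon". It goes on to refer to the post-operative period and then to the medical record. It does not say when capture begins.

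Section 8 contains several rules:
- Unexpected and/or serious events go to the monitoring committee (DSMAC) with a judgment of their relation to study procedures.
- Because patients having this surgery are expected to have complications and medical events, all adverse events are logged and reviewed, but the team will "evaluate and report on only those with outcomes that would not routinely be expected in this surgical patient population".
- An unexpected event triggers a study physician's review of the record. The study-file entry gives the dates of occurrence and resolution, the severity and the actions taken.
- A drug reaction goes to the IRB and FDA if it exceeds what open brain-tumor surgery would be expected to produce and is judged likely to be related to study procedures.

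None of these rules distinguishes events by time of onset.

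**The concern.** Once anesthesia and surgery begin, most events have an obvious competing explanation, and this open-label study has no control group to help separate the causes. The interval between injection and anesthesia is the one period after dosing in which the operation is ruled out as a cause. What is routine for the surgical population is therefore a poor test there of whether an event deserves a causality judgment.

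The information at stake is modest but hard to obtain elsewhere. Section 1.1 calls this the first-in-human trial in neurosurgery, and Section 1.4 says there are no clinical data on the product. Section 1.5 lets the dose rise to 3X and 6X on imaging results. A mild reaction soon after injection, if it resembles a common complaint in these patients, could be logged without anyone having to say whether the drug might have caused it.

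**Working it through.** The plan states no figure on this point, so there is nothing to reproduce. The check is to follow events through the rules.

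**Step 1: the interval.** There is one dose, given on the day of surgery (Section 5.2), about 60-180 minutes before either surgery (Section 5.4) or induction of anesthesia (Section 5.1). No other period in the study follows dosing and precedes the operation.

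**Step 2: three kinds of event with onset in the interval, under Section 8 as written.**
- *Serious.* The opening rule sends it to the committee with a relationship judgment, expected or not. The later sentence restricting evaluation and reporting conflicts with this if read literally, and the two need reconciling.
- *Non-serious and unexpected.* It goes to the committee, prompts physician review and is entered in the study file.
- *Non-serious and of a type judged expected.* It is logged and reviewed. Nothing requires evaluation or a relationship judgment.

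Only the third kind falls in the gap. Headache, nausea or a change in blood pressure might be examples, but the documents list no expected events.

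**Step 3: can the record show the order of events?** The entry described in Section 8 has a date only. Injection and surgery fall on the same date, so that entry cannot separate onset before surgery from onset after it. Section 5.1 does collect the time from administration to surgery, so a clock time of onset would be enough to place the event. The case report forms are not reproduced in the documents. They, or the medical record, may hold a time, but the protocol does not require one.

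**Step 4: does Section 6 close the gap?** It does not. It describes follow-up after the operation and does not state that capture starts at injection.

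**Step 5: figures for context only.**
- Section 1.3.2 reports: "The plasma half-life of ABY-029 in normal rats is approximately 15-20 minutes". The interval is then 60/20 = 3 to 180/15 = 12 rat half-lives. If humans resembled rats, much of the early plasma exposure would precede surgery. This is an extrapolation, and the same section describes a bi-exponential curve.
- With no events in n patients, the one-sided 95% upper bound on the event rate is 1 - 0.05^(1/n): 39.3% for n = 6, 28.3% for n = 9 and 22.1% for n = 12.
- The chance of at least one event is 1 - (1 - p)^n. For assumed true rates of 5%, 10% and 20% it is 26.5%, 46.9% and 73.8% with n = 6, and 46.0%, 71.8% and 93.1% with n = 12. If the filter left half of such events unassessed (an assumption the documents neither support nor exclude), the chance that at least one is assessed falls to 14.1%, 26.5% and 46.9% with n = 6, and to 26.2%, 46.0% and 71.8% with n = 12.

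The half-lives and bounds do not measure the gap, because they would be the same under perfect reporting. The last calculation shows only how a filter would act if it removed a given share.

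**The case against.** Four arguments on the other side carry weight.

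- **Nothing is discarded.** Every event is logged and reviewed, so a reader who infers that evidence of a drug reaction is lost goes beyond the text. What is missing is a required causality judgment for one class of event.
- **Serious events have their own route.** One might infer that the filter undermines the protocol's statement that drug-related serious events are not expected. It does not: the opening rule of Section 8 covers serious events whatever their expectedness, and non-serious events do not test a statement about serious ones.
- **The filter's rationale is largely post-operative.** A distinctive reaction in the holding area would probably be called unexpected and evaluated. This is a sensible reading, but the text does not state it. The filter refers to the surgical patient population and makes no exception by onset time.
- **The interval is not purely drug exposure.** Section 5.4 allows for another procedure: "If ABY-029 is administered prior to the pre-surgical MRI, a research nurse will accompany the patient to the MRI". The two anchors also leave it unclear whether anesthesia falls inside the interval. It is the best period available for attribution, but not a perfectly clean one.

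The defense can add that Section 5.1 counts subjects as enrolled from injection, that Section 6.2 makes pre-operative vital signs available for adverse-event monitoring, and that Section 1.5 says this is not a safety study. These points lower the weight of the concern. They do not supply the missing rule, because availability of data is not a requirement to assess an event.

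**Conclusion.** The concern holds in a limited form. As written, Section 8 does not require a judgment of relation to ABY-029 for a non-serious event of an expected type that begins between injection and anesthesia or surgery. The study-file entry it describes may also fail to show that onset came before surgery.

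The gap covers one class of event in a period of about 1-3 hours in 6-12 patients. The number of affected events cannot be estimated, since the documents give neither a list of expected events nor their rates. The conclusion assumes that Section 8 is applied literally and that no unpublished form or instruction adds a time field or a causality assessment. It does not depend on the rat half-life or on the zero-event bounds.

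This is a cheap improvement of modest weight. It does not mean that safety monitoring in the trial is invalid.

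**What to change.** In Section 8, state that the surgical-expectedness filter does not apply to adverse events with onset between the ABY-029 injection and induction of anesthesia. For those events, record the clock time of onset, assess relation to ABY-029 whatever the expectedness, and list them by dose level in the periodic summaries that Section 8 already provides for. Separate reporting of each minor event to the DSMAC is not needed.

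In Section 6, state that adverse-event capture starts at injection. Reconcile Sections 5.1 and 5.4 on whether the 1-3 hours end at induction of anesthesia or at surgery. Induction is proposed above only as a reporting boundary, because it keeps anesthesia effects out of the category. It does not settle which dosing anchor the protocol intends.

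The cost is protocol wording, one added field and relationship judgments on a few more minor events. No visit, test or extra staff is needed. Some recording would fall to Same Day Surgery or inpatient nurses who are not research staff, so brief instruction or delegation may be required.

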5.5 Subject Compliance Monitoring

Subjects participate in a “one-time” event (i.e., surgery) as part of this study and are monitored through the in-patient surgical service during the time of their participation.

5.6 Prior and Concomitant Therapy

This study is a Phase 0 diagnostic trial of ABY-029 fluorescence as a possible intraoperative imaging biomarker during open cranial surgery for tumor resection. Prior and/or concurrent medical therapies do not alter the diagnostic intent and/or endpoints associated with the study.

5.7 Packaging

ABY-029 is packaged as a transparent, green-blue liquid in 5mL glass vials at a concentration of 0.27 mg/mL, in PBS (phosphate-buffered saline). It is stored at the Investigational Pharmacy at Dartmouth-Hitchcock Medical Center (Address: Dartmouth Hitchcock Medical Center, Investigational Pharmacy, [name]). ABY-029 is shipped in clear glass vials, each with a rubber stopper in boxes containing 10 mL units.

5.8 Blinding of Study Drug

This study is a Phase 0 diagnostic trial of ABY-029 fluorescence as a potential intraoperative imaging biomarker during open cranial surgery for tumor resection and does not include comparison treatment groups. Because all subjects receive ABY-029, blinding of the surgeon to the study drug is not practical or appropriate.

5.9 Receiving, Storage, Dispensing and Return

5.9.1 Receipt of Drug Supplies

ABY-029 will be shipped to the Investigational Pharmacy at Dartmouth-Hitchcock Medical Center by UAB. Investigational pharmacy staff will count and verify that the shipment contains all the items noted in the shipment inventory, providing temperature monitoring data to UAB if necessary. Investigational pharmacy staff will document receipt into their electronic investigational drug management database that keeps a perpetual inventory. Any damaged or unusable study drug in a given shipment will be documented in the study files, and destroyed on site following standard procedures.

5.9.2 Storage

ABY-029 will be stored as a transparent, green-blue liquid in its shipment vials and outer carton in a freezer at temperatures between -15°C and -25°C. Vials will not be removed from the outer carton until drug is prepared as ABY-029, which must be stored under dark conditions.

5.9.3 Dispensing of Study Drug

Once drug assignment is performed, a study authorized staff member (e.g., [name], his designee) will order ABY-029 through the institution's electronic medical record. This order will specify the dose of 1X (237 µg), 3X (711 µg) or 6X (1.42mg) for ABY-029. Since the concentration in each vial of ABY-029 is 1.35 mg or 5.7X, in order to conserve our supply of ABY-029 we will administer a 5.7X dose to the 6X dose group in this study, and will call this the "6X dose" throughout this protocol. One dose of ABY-029 will be administered to each subject. The investigational pharmacy pharmacist will process this order and a pharmacy technician will prepare the ABY-029 dose as described in Section 5.4 (above)

5.9.4 Drug Accountability

When processing an order for ABY-029, an investigational pharmacy pharmacist will make an entry into the electronic investigational drug management database to remove vial(s) used to prepare a dose from ABY-029 drug inventory. A member of the study team will document the amount of ABY-029 administered and any amount remaining in the institution's electronic medical record.

5.9.5 Return or Destruction of Study Drug

At the completion of the study, a final reconciliation of drug shipped, drug consumed, and drug remaining will occur. This reconciliation will be logged on the drug reconciliation form, signed and dated. Any discrepancies noted will be investigated, resolved, and documented prior to return or destruction of unused study drug. Site policy (i.e., Investigational Pharmacy) is to destroy any used, open drug containers on site. Drug destroyed on site will be documented in the study files.

6 Study Procedures

This study is a Phase 0 clinical investigation of ABY-029 concentration measured/detected in brain tissue through its fluorescence emissions as an intraoperative biomarker of tumor during open cranial surgery for tumor resection. Subjects participate in a "one-time" event/visit (i.e., surgery) as part of this protocol. Images and data from the patient's pre- and post-operative MR scans are used for analysis in the study, but these acquisitions are part of the patient's standard-of-care, would occur independently of whether the participant is enrolled, and thus, are not considered to be research study visits. No post-surgical follow-up visit is part of the protocol data collection or analysis. Patients are monitored for possible adverse events for approximately 30 days through the routine follow-up under the care of the operating surgeon involved in

the study procedures, post-operatively, and subsequently through the medical record. Hence, this information is already being collected as part of standard-of-care and is available for adverse event surveillance.

